
1.5 Dose Rationale and Risk/Benefits

In our systematic review of the literature on the use of BTX-A with subpectoral breast implants²⁴, the dose of BTX-A administered to each patient in various studies ranged from 75 units to 200 units per breast. BTX-A was injected into the pectoralis major muscle alone in four studies, while in the study published by Layeeque et al., the toxin was injected in the pectoralis major muscle, serratus anterior and rectus abdominis muscle insertion of each breast. Richards et al. injected BTX-A in the pectoralis major muscle and subcutaneous tissues of the breast.

Based on these data, we concluded that an injection of 100 units of BTX-A per breast is a prudent choice. This dosage is also the standard dose used for several clinical indications, such as strabismus. In one study, 500 units of BTX-A were injected in the pectoralis major muscle of patients suffering of spastic shoulder pain after a cerebrovascular accident, and according to the authors, no important adverse event occurred.¹⁸

We have opted for an intra-operative injection rather than a pre-operative injection prior to surgery to minimize a theoretical risk of tumor seeding from percutaneous needle injection. **The BTX-A injection will be performed intra-operatively under general anesthesia, after all irrigations of the surgical site are completed, BUT prior to the placement of the tissue expander under the pectoralis major muscle to avoid any inadvertent puncture of the prosthetic device. BTX-A will be given only once during surgery and will not be repeated postoperatively.** The reason for giving the injection during the surgery is that it will allow the anti-nociceptive action of BTX-A to take effect immediately while the paralytic action will take about 7 to 10 days to take effect, thus coinciding with the start of tissue expansion. Furthermore, since the pectoralis major muscle is large and easily accessible, intra-muscular injection will be ascertained during surgery as it will be performed under direct visualization of the muscle. The clinical effects of a single injection of BTX-A usually lasts 3-4 months.²⁸ On average, the duration of tissue expansion usually ranges between 1 and 4 months. Therefore, our study design is based on a single intraoperative injection of BTX-A, and no repeat injection will be performed on patients enrolled in this study.

Safety, Risks and Adverse Effects:

BTX-A has been used as a therapeutic agent since the late 1970s. Since then, it has been demonstrated to be a remarkably safe drug when used under medical supervision.^{27, 28} The mechanism of action of BTX-A has been extensively studied and is known to be very specific. Thus, non-neuromuscular adverse effects and systemic side effects are very rare.²⁹

Local side effects of BTX-A injection include a flu-like syndrome that is generally short-lived, dysphagia, and xerostomia. Unintended weakness of the muscle injected or of nearby muscles could also be a negative effect. Other potential side effects include muscle soreness, rash, headaches, light-headedness, fever, chills, hypertension, diarrhea and abdominal pain.

Potential risks with this therapy include a distant spread of BTX-A effect from the area of injection to produce symptoms consistent with systemic botulinum toxin effects. These symptoms have been reported hours to weeks after injection of BTX-A. Life threatening adverse events such as swallowing and breathing difficulties can occur, and there have been reports of death. The risk of these symptoms is probably greatest in children treated for spasticity, but the effects of distant toxin spread can also

occur in adults, particularly in those patients who have underlying conditions that would predispose them to these symptoms.

All serious adverse effects will be reported. The PI and the research team will continually review blinded data after each subject has study interaction, including a review of all adverse events, to determine seriousness and relation to study drug. Minor adverse events and unusual complications encountered during the period of tissue expansion will be carefully recorded. In the event of a serious adverse reaction to the treatment, the study participant will be treated accordingly depending on the reaction.

We consider that the risk level to subjects enrolled in this study is greater than minimal risk, yet not disproportionate in relation to the anticipated benefits and/or knowledge that might reasonably be expected from the results. Potential benefit for study participants is an improved pain management during the period of tissue expansion. BTX-A has been used as a therapeutic agent since the late 1970s. Since then, it has been demonstrated to be a remarkably safe drug when used under medical supervision.^{27, 28} The median lethal dose is estimated to be approximately 39 units of BTX-A per kilogram of body weight.²⁶ The mechanism of action of BTX-A has been extensively studied and is known to be very specific. Thus, non-neuromuscular adverse effects and systemic side effects are very rare.²⁹

By performing a study that accurately evaluates the effect of BTX-A on women's subjective pain and physical well-being assessments during the expansion period of implant-based breast reconstruction, information on a critical aspect of HRQoL will be obtained. If our expected outcomes are met, BTX-A could become part of the standard of care for women undergoing breast reconstruction with tissue expanders. Future studies in this continuum of research will include: 1) the determination of the minimal effective dose of BTX-A required for appropriate pain management during tissue expansion; 2) an economic evaluation of this therapy; and 3) a comprehensive evaluation of all aspects of patient satisfaction and HRQoL associated with the use of this therapy in tissue expansion, and the overall outcomes of breast reconstruction.

2 Study Objectives

Overall Aim: The proposed study will be the first, multi-center, double-blinded PRCT evaluating the efficacy of BTX-A in alleviating pain and improving health-related quality of life (HRQoL) during the period of tissue expansion. Results from this study will provide preliminary information on the efficacy of BTX-A in this population. This base of knowledge will contribute to advances in quality of health care provision, will guide plastic surgeons in applying evidence-based practices, and support patients and surgeons in the process of shared decision-making.

Primary Objective

Specific Aim: To determine the effect of BTX-A on pain and physical well-being during the expansion period in women undergoing subpectoral placement of tissue expanders for two-stage implant-based breast reconstruction.

Hypothesis: We hypothesize that intra-operative infiltration of BTX-A in the pectoralis major muscle reduces pain associated with tissue expansion, and improves women's physical well-being and HRQoL.

Expected Outcomes: Upon completion of the proposed study, it is our expectation that we may demonstrate an improvement in patient-reported outcomes with the use of BTX-A. We anticipate that the improvement gained with this therapy will outweigh the potential adverse events experienced. This would be in agreement with the documented findings in other areas.⁴³ More specifically, we believe that we may reveal the positive impact of BTX-A on patient-rated pain and a clinically meaningful benefit on physical well-being in this population, when compared with placebo (control group). Thus, important advances in the management of pain associated prosthetic breast reconstruction techniques could be expected, which could ultimately reduce the physical impact of implant-based reconstruction and improve QoL for breast cancer survivors.

3 Study Design

3.1 General Design

EXPERIMENTAL DESIGN FOR SPECIFIC AIM#1: To determine the effect of BTX-A on pain and physical well-being during the expansion period in women undergoing subpectoral placement of tissue expanders for two-stage implant-based breast reconstruction.

Research Design: The study design chosen to test our working hypothesis and answer our specific aim is a multi-center, double-blinded, placebo-controlled, prospective, randomized trial. Women at least 18 years of age, who will undergo immediate unilateral or bilateral tissue expander reconstruction, will be recruited to participate in the study.

Consecutively enrolled eligible women will be randomized into one of two different treatment groups, described in section 5.3. Expected duration of subject participation is 4 months.

Study Timeline and Feasibility:

PROPOSED PROJECT TIMETABLE				
AIMS/TASKS	YEAR 01	YEAR 02	YEAR 03	YEAR 04
Specific Aim #1:				→
• Enrollment		→		
• Follow-up		→		
Data Analysis			→	→

For this study, we plan to accrue up to 134 patients in order to obtain a sample size of 128 subjects (64 women per group). Based on annual operative volumes at Mayo Clinic Rochester, and considering that not all plastic surgeons performing tissue expander breast reconstruction will be contributing to

the study, we estimate that approximately 150 women will be eligible for recruitment over a 36-month period, ensuring the feasibility of adequate sample size recruitment (see table below).

Annual numbers of breast reconstructions with tissue expanders at Mayo Clinic Rochester (2008-2010)

Procedure Year	Unilateral tissue expander breast reconstruction	Bilateral tissue expander breast reconstruction	TOTAL
2008	98	123	221
2009	74	111	185
2010 (10 months)	70	107	177

We anticipate that these numbers will remain approximately constant. It is estimated that subjects will be recruited over a 40-month period, and each participant will be followed for 4 months with data collected longitudinally over this period. The last women enrolled in year 1 will be followed for 4months into year 2. Data analysis will commence in year 2.

3.2 Primary Study Endpoints

The primary study endpoint is to determine the efficacy of a single intra-operative injection of BTX-A in the pectoralis major muscle on pain and physical well-being in women undergoing tissue expansions following mastectomy and immediate tissue expander breast reconstruction.

The outcome measures selected to test our working hypothesis and answer our specific aim #1 are a numeric pain intensity scale (NPIS)⁷¹, and the Physical Well-Being scale of the BREAST-Q®: Reconstruction Module. The NPIS is a reliable and valid tool that is widely used as a measure of pain intensity (See Appendix for complete scale). To assess physical well-being, we selected the 16-item Physical Well-Being scale from the BREAST-Q®: Reconstruction Module. The BREAST-Q® is a newly-developed and validated PRO measure designed to measure patients' perception of outcomes following breast surgery.⁷² The Reconstruction Module consists of scales in six domains related to satisfaction and QoL (See Appendix for complete scale). The Physical Well-Being scale has items that relate to issues surrounding chest and upper body symptoms, and how these impact on physical function and participation in activities before and after breast reconstruction. Study participants will answer how often they have experienced each symptom during the previous two-week period, using a 5-point Likert scale (1 – none of the time, 5 – very often). Answers from these questions will be combined to provide a total physical well-being score for each patient at each follow-up visit. Average scores for both study groups will be compared. These two measures will be administered at the pre-operative visit, the first postoperative visit (1-2weeks) and subsequent Plastic Surgery appointments/expansion visits until the end of study is reached. After much consideration, we have made the decision not to ask enrolled subjects to record the amount of oral analgesic medication taken

daily during the course of the study, as this method is often inaccurate due to missing data entries, and would therefore yield unreliable results. Furthermore, the randomization process in this study should ensure a random distribution of patients with different oral analgesics intakes. It was also felt that not recording the amount of oral analgesic medication would reduce the burden of study participants.

3.3 Secondary Study Endpoints

Secondary study endpoints will include:

- 1) The initial percent volume expansion (defined as initial intraoperative fill volume divided by manufacturer recommended total tissue expander volume);
- 2) The rate of tissue expansion between the BTX-A group and the placebo group, with or without the use of ADM;
- 3) Rate of reconstructive failure (tissue expander removal for any reasons, such as infection or uncontrolled pain).

3.4 Primary Safety Endpoints

The primary safety endpoints of this study is the incidence of side effects attributable to the injection of BTX-A at doses of 100 units and 200 units, in women undergoing immediate post-mastectomy breast reconstruction with tissue expander(s).

Patients will be advised to inform the Principal Investigator and the study coordinator immediately if they develop any unusual symptoms (including difficulty with swallowing, speaking, or breathing), or if any existing symptom worsens. Patients will also be counseled that if loss of strength, muscle weakness, blurred vision, or drooping eyelids occur, they should avoid driving a car or engaging in other potentially hazardous activities.

At each follow-up visit, the study coordinator will question study subjects about occurrence of adverse events. All serious adverse experiences will be collected and reported. Local side effects of BTX-A injection include a flu-like syndrome that is generally short-lived, dysphagia, and xerostomia. Unintended weakness of the muscle injected or of nearby muscles could also be a negative effect. Other rare potential side effects include muscle soreness, rash, headaches, light-headedness, fever, chills, hypertension, diarrhea, abdominal pain, swallowing and breathing difficulties. Furthermore, the status of wound healing and tissue integrity will be performed at the first postoperative visit for all patients (i.e., at one to two weeks following surgery).

4 Subject Selection Enrollment and Withdrawal

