5.2 Treatment Regimen

A single intramuscular injection of 100 units of BTX-A will be done intra-operatively in the pectoralis major muscle. This injection will not be repeated during the course of the study. Thus, women undergoing unilateral tissue expander placement will receive a dose of 100 units of BTX-A, whereas women undergoing bilateral tissue expander placement will receive a dose of 200 units of BTX-A for the purpose of this study.

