5.3 Method for Assigning Subjects to Treatment Groups

Methods: Consecutive women who elect to pursue breast reconstruction with tissue expanders will be approached to participate in this study. All consenting subjects will be randomized to receive either a single dose of 100 units of BTX-A per breast, or a placebo. Study participants will not be blinded regarding the use of ADM at the time of surgery.

Treatment group assignment:

STUDY ARMS	ASSIGNED TREATMENT
1	BTX-A +/- ADM
2	Placebo +/- ADM

Randomization and Masking: Treatment blinding and randomization will be carried out in the hospital's Research Pharmacy Service using a program to generate random numbers. The injected solutions of BTX-A and placebo (0.9% Sodium Chloride Injection USP) will be prepared by the pharmacy service to ensure masking. At the time of injection in the pectoralis major muscle, neither the treating surgeon nor the study participants will be aware of group allocation with regards to the use of BTX-A or placebo. All research team members involved in the assessments and analysis of the data will be blinded. Thus, only the pharmacy personnel preparing the syringes will be aware of group assignment (Group A or B).

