All unresolved adverse events should be followed by the investigator until the events are resolved, the subject is lost to follow-up, or the adverse event is otherwise explained. At the last scheduled visit, the local investigator should instruct each subject to report, to the local investigator, any subsequent event(s) that the subject, or the subject's personal physician, believes might reasonably be related to participation in this study. The local investigator should notify the study regulatory sponsor of any death or adverse event occurring at any time after a subject has discontinued or terminated study participation that may reasonably be related to this study. The sponsor should also be notified if the local investigator should become aware of the development of problems, cancer or of a congenital anomaly in a subsequently conceived offspring of a subject that has participated in this study.

Hospitalization, Prolonged Hospitalization or Surgery

Any adverse event that results in hospitalization or prolonged hospitalization should be documented and evaluated for relationship to the study drug/placebo. If there is a reasonable possibility that it is related to the study drug/placebo then will be reported as a serious adverse event unless specifically instructed otherwise in this protocol. Any condition responsible for surgery should be documented as an adverse event if the condition meets the criteria for an adverse event.

Neither the condition, hospitalization, prolonged hospitalization, nor surgery are reported as an adverse event in the following circumstances:

- Hospitalization or prolonged hospitalization for diagnostic or elective surgical procedures for a preexisting condition. Surgery should **not** be reported as an outcome of an adverse event if the purpose of the surgery was elective or diagnostic and the outcome was uneventful.
- Hospitalization or prolonged hospitalization required to allow efficacy measurement for the study.
- Hospitalization or prolonged hospitalization for therapy of the target disease of the study, unless it is a worsening or increase in frequency of hospital admissions as judged by the clinical investigator.

The expected adverse events from surgery include post-operative pain, nausea, vomiting, general anesthesia risks, hemorrhage, surgical site infection, mastectomy skin necrosis, seroma, surgical site paresthesia.

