8.2 Recording of Adverse Events

At each contact with the subject, the investigator must seek information on adverse events by specific questioning and, as appropriate, by examination. Information on all adverse events should be recorded immediately in the source document, and also in the appropriate adverse event section of the case report form (CRF). All clearly related signs, symptoms, and abnormal diagnostic, laboratory or procedure results should be recorded in the source document.

All adverse events occurring during the study period must be recorded. The clinical course of each event should be followed until resolution, stabilization, or until it has been ultimately determined that the study treatment or participation is not the probable cause. Serious adverse events that are still ongoing at the end of the study period must be followed up, to determine the final outcome. Any serious adverse event that occurs after the study period and is considered to be at least possibly related to the study treatment or study participation should be recorded and reported immediately.

Adverse events will be monitored and recorded during the four month postoperative time period.

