8.4 Unblinding Procedures

In case of an adverse event, un-blinding of the study participant will be carried out immediately. The event will be analyzed in the same manner as any severe adverse drug reaction. This will be reported to the appropriate agencies with the analysis, conclusions and recommendations. The study will then

be re-instituted if given approval to continue. This study subject will be categorized as a treatment failure and imputed the most negative score on all outcomes.

All serious adverse events (SAE) will be reported, and un-blinding will be part of managing an SAE. The PI and the research team will continually review blinded data after each subject has study interaction, including a review of all adverse events, to determine seriousness and relation to study drug. Minor adverse events and unusual complications encountered during the period of tissue expansion will be carefully recorded. In the event of a serious adverse reaction to the treatment, the study participant will be treated accordingly depending on the reaction.

Any AE that occurs during the course of the study will be disclosed to the Mayo Clinic IRB. All SAE will be reported to the FDA as well as to Allergan within 15 calendar days after its first knowledge. The Principal Investigator will provide written notice to Allergan within 15 calendar days of any occurrence(s) of either (i) pregnancy or (ii) lactation during the time period of effect of BOTOX®, which can last three to four months.

In cases where un-blinding was not associated with an SAE, such actions will be reported in a timely manner. Notification of sponsor will be performed within 24 hours by phone or fax, followed by a written narrative of the event within 48 hours. The statistician conducting the interim analysis will contact Research Pharmacy personnel to proceed with un-blinding not associated with an SAE.

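### The primary safety endpoint is limited to side effects judged attributable to BTX-A, names no placebo comparison and has no stated analysis; its dose labels cannot be read as a dose effect

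*Combined protocol and SAP*

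**What the plan says.** Section 3.4 gives the primary safety endpoint as "the incidence of side effects attributable to the injection of BTX-A at doses of 100 units and 200 units", and section 7.1 repeats it. Neither section names a comparator, a contrast, an interval, or who decides attribution. Section 7.2 sets out tests under its primary and secondary hypotheses but does not mention safety.

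On dose, section 5.2 says that "women undergoing unilateral tissue expander placement will receive a dose of 100 units of BTX-A" and that "women undergoing bilateral tissue expander placement will receive a dose of 200 units of BTX-A". Under section 5.3 women are "randomized to receive either a single dose of 100 units of BTX-A per breast, or a placebo". The randomised factor is therefore drug or saline, not dose. Allocation is made "using a program to generate random numbers", with no stratification by laterality stated.

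On collection, section 8.2 requires that "All adverse events occurring during the study period must be recorded", over four months after surgery. Section 8.1 adds that "The expected adverse events from surgery include post-operative pain, nausea, vomiting, general anesthesia risks", followed by haemorrhage, infection, skin necrosis, seroma and paresthesia.

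On blinding, section 8.4 opens with "In case of an adverse event, un-blinding of the study participant will be carried out immediately". The same section, like section 1.5, also says that the research team reviews blinded data to decide seriousness and relation to study drug.

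**The concern.** A randomised saline arm makes case-by-case causality calls unnecessary: the excess over placebo is the drug's contribution. An endpoint built on attribution gives that up. Section 3.4 lists muscle soreness, rash, headache, light-headedness, fever, chills, hypertension and abdominal pain as possible BTX-A effects. In a woman just after mastectomy, general anaesthesia and subpectoral expander placement, few of these can be assigned to one cause with confidence. Error can run both ways: surgical symptoms counted as toxicity, and real toxin effects put down to surgery.

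If the arm is known when the call is made, the error becomes lopsided, because a woman known to have had saline cannot have a BTX-A side effect.

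Reporting incidence under two dose labels adds a second hazard. The 200-unit women have two operated breasts and the 100-unit women have one. Section 4.1 admits prophylactic cases only when bilateral, so the indication differs too. Section 2 expects benefit to outweigh adverse events. That is an expectation, not a planned analysis, but supporting it needs an unbiased estimate of excess risk.

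**Working it through.** **1. The plan's own figures.** The documents give no rate, margin or sample size for safety. The 64 per arm in section 7.1 is a pain calculation (difference 1.0, SD 2.0, two-sided 0.05). It reproduces with a two-sample t-test at 80.1% power, and is used below only as the number of women per arm.

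**2. Dose and laterality.** The site volumes in section 3.1 give (123 + 111 + 107)/(221 + 185 + 177) = 341/583 = 58.5% bilateral. If the trial has the same mix, 64 × 0.585 ≈ 37 BTX-A women receive 200 units and 64 − 37 = 27 receive 100 units. Within the BTX-A arm, dose and laterality are the same variable, so no adjustment can separate them.

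**3. Reading the two incidences as a dose effect (assumed rates).** Suppose that BTX-A does nothing and background rates depend only on surgery.

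| Unilateral | Bilateral | 200 U minus 100 U | Chance of nominal significance, 27 v 37 | BTX-A minus placebo within laterality |
|---|---|---|---|---|
| 10% | 20% | 10 points | 18% | 0 |
| 10% | 30% | 20 points | 48% | 0 |

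The last column is the expected value of the contrast that randomisation supports.

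**4. Attribution with the arm known (assumed rates).** Take a background of 20–40% in both arms, half of events called attributable in BTX-A women and none in saline women. The endpoint then reads 0.20 × 0.5 = 10% to 0.40 × 0.5 = 20%, against 0%, with zero true excess. As counts, about 6/64 v 0/64 (Fisher p ≈ 0.03) to 13/64 v 0/64 (p ≈ 0.0001). This is a worst case: every call follows unblinding.

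**5. What a by-arm analysis can show.** The approximate 95% half-width for a difference, with rate p in both arms, is 1.96 × √(2p(1 − p)/n). At an assumed p = 10%:

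- overall, n = 64: ±10 points
- unilateral, n = 27: ±16 points
- bilateral, n = 37: ±14 points

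With 10% on placebo, the BTX-A rate detectable at 80% power is 29.6% overall, 43.0% in unilateral women and 37.3% in bilateral women. The within-laterality contrasts can therefore only be descriptive.

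**The case against.** A reader might infer that the trial ignores the placebo arm for safety. The documents do not support that. Section 8.5 has a stopping rule that compares surgical site infection rates between arms. Section 8.6.1 gives unblinded adverse event data to an uninvolved statistician at the interim. Sections 8.1 and 8.3.2 consider relation to study drug or placebo. The Précis and section 7.2 provide for chi-square or Fisher tests by treatment group. All of this stands, but none of it defines or analyses the primary safety endpoint, and the generic tests are introduced for outcome variables without naming safety.

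A reader might also infer a planned comparison of 200 with 100 units. There is none; the doses may simply describe the exposures. The hazard lies in how the two figures would be read.

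It can be argued that attributable means the excess over placebo. The wording allows that, but no such contrast is stated, and sections 1.5 and 8.4 describe relatedness as decided by the research team.

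Nor do the documents show that every call is made with the arm known. Section 8.4 also describes blinded review, and its later text ties unblinding to serious events. This limits step 4 to an illustration. The conflict within section 8.4 remains, and blinded attribution is not assured.

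Finally, any adverse event could be nearly universal after mastectomy and would then hide a toxin effect. That is correct and shapes the fix.

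**Conclusion.** The concern holds for the definition and analysis of the primary safety endpoint. As written, the endpoint depends on attribution that is unreliable after this surgery and may be made unblinded. It names no placebo contrast, and section 7.2 has no analysis for it. The two dose-labelled incidences cannot be read as a dose effect, because dose is fully determined by laterality. Even the within-laterality contrasts with placebo estimate each regimen in its own surgical group, not a dose-response.

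The structural points follow from the text alone. The sizes do not: the 10–20 point figures rest on assumed event rates, and the split of 27 and 37 assumes that the trial mirrors site volumes. The direction and size of any actual bias cannot be established from the documents.

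**What to change.** - **Endpoint (3.4 and 7.1).** Restate it as the incidence of each listed BTX-A side effect through month 4, by randomised arm, regardless of judged attribution. Give any adverse event as a supporting summary only.
- **Analysis (7.2).** Add the BTX-A minus placebo difference with 95% CI for each listed side effect overall. Show the same descriptively within unilateral women (100 units or saline) and bilateral women (200 units or saline). State that the 100-unit and 200-unit incidences are not a dose comparison.
- **Attribution.** Keep it as supportive, recorded before any unblinding of that woman, and say who makes the call.
- **Section 8.4.** Reconcile the immediate unblinding statement with the blinded review of relatedness.

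The cost is protocol wording and one table. All adverse events are already recorded in both arms, and laterality is known from surgery, so no extra patients or data are needed. Raw rates will look higher in both arms, and within-laterality intervals will be wide.
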